#### 3. Abstract:

Although compelling evidence exists that high doses of mother's own breast milk (mother's own milk; MOM) improves infant health, breast pump dependent (need to use a breast pump to obtain milk for infants too ill or preterm to breastfeed) mothers of critically ill infants often provide insufficient amounts of MOM to support these benefits. Insufficient MOM has its origins during the first 14 days postpartum, a critical window that includes secretory activation (SA; milk coming in; lactogenesis II) and the achievement of coming to volume (CTV; providing ≥ 500 mLs/day of MOM by day 14 postpartum). For all lactating mothers, SA must be achieved for lactation to continue, and achievement of CTV predicts provision of MOM through to neonatal intensive care unit (NICU) discharge in preterm very low birthweight (VLBW; <1500 g birthweight) infants. For this study, we posit that alternate breast pump suction patterns (BPSP; suction rate, intensity, and rhythm) may facilitate achievement of CTV in mothers who have achieved SA, but whose daily pumped MOM volumes indicate a high risk of not achieving CTV. Therefore, the overall objective of this study is to compare the clinical effectiveness of three different breast pump suction patterns on lactation outcomes, including achievement of SA, among pump dependent mothers of critically ill infants who demonstrate faltering lactation after achievement of SA. At 6-8 days postpartum, 90 pump dependent mothers of critically ill infants who have achieved SA, but demonstrate faltering lactation (<350 mLs/day pumped MOM volume), will be randomized to use one of three different BPSPs with two groups having alternative BPSPs and one group using the current practice standard for 7 days. Study outcomes will include the following; (1) pumped milk volume, (2) secondary lactation outcomes (whether or not mothers achieve CTV by day 14-15 postpartum, maintenance of secretory activation, MOM removal efficiency, and lactation duration); (3) maternal perceptions of comfort, effectiveness, efficiency, and convenience of the BPSPs, and (4) proportion of feedings consisting of MOM consumed by infants. Two exploratory aims will explore potential benefits of the 3 BPSPs on lactation outcomes of mothers with co-morbidities known to negatively affect the above-mentioned lactation outcomes and whether mothers at risk of suboptimal lactation who use an alternate BPSP achieve the same lactation outcomes as do mothers who do not demonstrate faltering lactation.

However, mothers of critically ill infants in the NICU have multiple barriers to achievement of these biologic processes, including complete breast pump-dependency, meaning that the pump rather than the infant removes MOM and regulates continued lactation. Thus, these mothers are often unable to provide adequate MOM volume for infant feedings, compromising infant health. In particular, lack of achievement of CTV is the primary predictor of no MOM feeding at NICU discharge, and the window between achievement of SA (on average day 5.6 postpartum in breast pump-dependent mothers of preterm infants) and achievement of CTV on day 14-15 postpartum represents a short, but critical window for intervention in this population. Although breast pump-dependency is not modifiable, the type of breast pump, BPSPs, and mothers' use of the pump are modifiable factors that can potentially improve the achievement of CTV and subsequent longer-term lactation outcomes. In particular, during the transition from the endocrine (SA) to autocrine control of lactation, frequent and effective/efficient MOM removal is key to optimizing prolactin release from the brain, as well as leveraging the multiple autocrine and paracrine mechanisms that control continued MOM synthesis and release. Thus, modification of BPSPs that may optimize the effectiveness and efficiency of MOM removal between achievement of SA and CTV represents a promising "next step" intervention in this at-risk population.

The Role of Alternate BPSPs. Because critically ill infants admitted to the NICU are physiologically unable to fully feed directly at the breast, mothers are completely breast pump-dependent, meaning that they must use a breast pump to obtain MOM for their infant. Furthermore, in completely breast pump-dependent mothers, the pump rather than the infant regulates lactation processes, including suckling-induced prolactin release and the autocrine-paracrine mechanisms of "supply and demand". Thus, the pump must do more than just "get the MOM out" if lactation is to continue via these endocrine and autocrine mechanisms. Central to this concept is that the BPSP should mimic the healthy term infant during breastfeeding to the extent possible so that breast pump-dependent mothers receive mammary signaling that optimizes MOM synthesis and release. Previous studies reveal that the human infant uses species-specific sucking patterns during the early postpartum period as MOM volume is established. A member of this study team ([name]) partnered with Medela in 2008-2012 to create a BPSP that mimicked the human infant during the initiation of lactation. An RCT of 105 mothers demonstrated that the initiation BPSP resulted in significantly greater cumulative MOM volume during the first 14 days, and was significantly more efficient in MOM removal, saving important minutes for breast pump-dependent mothers. 11 This initiation BPSP is now embedded in Medela pumps throughout the world for use in the maternity setting, with instructions to use this BPSP (Plus) until the achievement of SA, then to switch to a Symphony plus 2-phase pattern which is a "one size fits all" approach to MOM removal.

**BPSPs 1** and 2. The current study posits that two alternative BPSPs may be more effective in increasing pumped milk volume and thus achievement of CTV in breast pump-dependent mothers by offering alternatives to the "one size fits all" approach of using the standard care Symphony Plus BPSP after achievement of SA. Eligible mothers will have demonstrated faltering lactation (<350 mLs/day pumped MOM on postpartum day 6-8) after achievement of SA. Both BPSP 1 (slower rate with a long hold time and higher starting vacuum pressure) and BPSP 2 (faster rate with longer hold time during peak vacuum pressures) have been trialed in mothers of preterm infants, but not during this early postpartum time period nor with mothers who experience faltering lactation. Although different in the manner in which suction is applied and maintained during each pump cycle, both BPSPs have greater area under the suction curve (accomplished via modifications in suction pressure and duration) than does the standard Symphony Plus BPSP. Theoretically, these BPSPs afford "more time" per cycle for MOM removal, and may optimize endocrine and autocrine regulation of lactation, increasing MOM synthesis. These outcomes are reflected in the specific aims. An additional interest is whether these alternative BPSPs may be especially effective and/or efficient in mothers with co-morbidities such as overweight and obesity, for whom the extra area under the suction curve may improve MOM removal. However, equally important is maternal perceptions of comfort and ease of use for both BPSPs, especially during the early postpartum period when the mammary tissues are more prone to discomfort with either breastfeeding or breast pump use.

## 5. Specific Aims:

The **primary purpose** of this study is to compare the clinical effectiveness of three different BPSPs [BPSP1, BPSP2, and Symphony Plus (Standard Care)] on lactation outcomes among pump dependent mothers of critically ill infants with faltering lactation.

## Specific aims are as follows:

**Aim 1**: Compare the clinical effectiveness of 3 different BPSPs on pumped milk volume during Days 8-15 postpartum.

**Aim 2:** Compare lactation outcomes for the three groups, including 1) maintenance of SA through to postpartum day 14-15, 2) rate of increase in daily pumped MOM volume, 3) whether or not mothers achieve CTV by day 14-15 postpartum, 4) cumulative pumped MOM volume over days 1-7 and 8-15) MOM removal efficiency, and 5) lactation duration.

Aim 3: Compare maternal perceptions of comfort, effectiveness, efficiency, and convenience of the 3 BPSPs.

**Aim 4:** Compare infant outcomes for the including: 1) proportion of feedings consisting of MOM during the NICU hospitalization, 2) proportion discharged consuming any MOM, and 3) proportion receiving MOM at 3 and 6 months of life.

**Exploratory Aim 1**: Explore potential benefits of the 3 BPSP on lactation outcomes of mothers with comorbidities known to negatively affect lactation outcomes (high BMI/obesity, diabetes, pregnancy induced hypertension).

**Exploratory Aim 2**: Explore whether mothers categorized as having faltering lactation on postpartum day 6-8 and who use BPSP1, BPSP2, or Symphony Plus BPSP (Standard Care) achieve the same lactation outcomes (Aims 1, 2, 4) as do mothers who do not demonstrate faltering lactation at postpartum day 6-8.

#### 6. Research Plan:

This study will use a randomized control trial design with 3 arms to compare the clinical effectiveness of three different BPSPs on lactation outcomes among pump dependent mothers of critically ill infants who demonstrate faltering lactation on day 6-8 postpartum. Mothers identified as having faltering lactation will be randomly assigned to one of 3 groups; (1) BPSP1, (2) BPSP 2, and (3) Symphony Plus BPSP (Standard Care).

## Sample and Setting:

Up to 274, racially and economically diverse mothers and infants(s) who have delivered a critically ill infant(s) admitted to the NICU will be sampled from the obstetrical unit at UFHealth Shands Hospital which is associated with a Level IV (72 bed) NICU.

Inclusion criteria are: 1)  $\geq$  18 years of age, 2) delivered infant(s) of any GA admitted to the NICU including mom of multiples, 3) intent to provide exclusive MOM to their infants for the first 14 days, 4) expected to be breast pump -dependent for at least 14 days, and 5) English speaking.

Exclusion criteria are: 1) breast reduction or augmentation, 2) infant not expected to survive, 3) medications or maternal conditions incompatible with providing MOM for a NICU infant, and (4) resides over 60 miles from UFHealth.

The NICU at UF Shands admits infants that are racially diverse regardless of private or Medicaid insurance coverage. All mom that meets the above criteria would be eligible for enrollment. Informed consent will be obtained by mothers in their postpartum hospital room or in the NICU while visiting their infant prior to 48 hours postpartum. The informed consent includes mother's permission to access their infant's chart to collect information up until infant's discharge. The infant has no study interventions. In the rare instance that an infant breastfeeds, intake will be determined through test weighting (infant weight pre and post breastfeeding). Prior to the mother's hospital discharge, she will be provided an empty payment card where participants will receive compensation, by adding payments for completing study events, listed below. After enrollment, a 2-minute maternal interview will be used to collect information to determine pre-pregnancy BMI and other factors that might impact lactation success (Appendix B). Information will be collected related to pumping frequency and pumped milk volume prior to enrollment (Appendix I). All enrolled mothers will be provided breast pumping instructions to optimize their pumping behaviors prior to achievement of secretory activation. This 30-minute optimization session will be provided by a Research Nurse Coordinators, who is also an International Board-Certified Lactation Consultant (IBCLC). The instructions will be standardized using a score card, which provides prompts for education discussion and video links about pumping practices, breast and nipple assessment, breast shield sizing and comfort. (Appendix F). A daily sample of 0.3 mL of pumped MOM (if mother has pumped at least 5mL/day) will be tested for MOM sodium level as an indicator of secretory activation. At day 6-8 postpartum, mothers at high risk of suboptimal lactation will be identified and randomized to one of three BPSPs Mothers will be determined to be at risk if they have (1) achieved secretory activation (change from small volumes of colostrum to large volumes of more mature milk; determined by a milk sodium level < 20 mM) and (2) have a pumped milk volume < 350 mL/d. Mothers who are identified as being not at risk for suboptimal lactation (have achieved secretory activation and their pumped milk volume is > 350mL/d) will not be randomized but will continue with standard care regarding BPSPs, and continue to have data regarding lactation collected. Mothers who do not reach SA, determined by a milk sodium level > 20 mM, will be withdrawn from the study and referred to the UF Shands Lactation Team. All mothers that achieve SA, will be provided a second 30-minute standardized breast pumping optimization session with instructions by a Research Nurse Coordinator who is an IBCLCs at day 6-8 postpartum. Mothers will complete the Maternal Perceptions Survey (Appendix K/Part A only) before starting new pattern. If randomized, Moms will complete the Maternal Perception Survey (Part A/B) on Day 9-11. A score card, designed for mothers who have already achieved secretory activation, includes educational prompts and video links regarding milk volume, pumping behaviors, breast and nipple assessment, flange fit and comfort will be utilized. (Appendix G). Should a mother be unable to obtain transportation to the NICU, they will be provided transportation through Uber Health, provided they live within a 60-mile radius of UF Shands due to cost limitation of study.

Mothers will be provided a payment card for amount listed following completion of the listed study event(s).

- 1. All mothers enrolled: optimization pumping session with the study Research Nurse Coordinator IBCLC, completion of the first MAACL, maternal interview, and lactation experience questionnaire. (\$25.00)
- 2. All mothers that achieve SA: Following completion of the second pumping optimization session with the study Research Nurse Coordinator IBCLC and completion of Maternal Perceptions Survey (Part A only) (\$25.00)
- 3. All mothers that do not reach SA, will be withdrawn from the study and not eligible for further compensation.

4. Following completion of the second MAACL, lactation experiences survey, maternal perception survey (if randomized) and return of all "loaned" breast pumps (\$50.00)

Total Compensation: Moms withdrawn at Week 1 (did not reach SA) \$25.00. All other moms (reaching SA) will receive up to (\$100)

**Sample Size Determination:** With 30 dyads (mom and infants) will randomized, using the block method, to each intervention group (2 alternate, one standard care), assuming a = 0.02 (Type I error rate), two-sided; independent sample t-test comparison of means (adjusted for multiple comparison between 3 groups); equality of variance between groups with 30 mothers per group we will have 80% power to detect a difference of 300 ml (effect size of 0.84; sd=350.0) between the groups.

**Randomization:** Those mothers who have been identified as being at high risk for suboptimal lactation will be randomly assigned using Block randomization to use one of three different BPSPs [BPSP1, BPSP2, or Symphony Plus BPSP (Standard Care)] for 7 days.

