**Aim 3:** Will compare maternal perceptions of comfort, effectiveness, efficiency, and convenience of the 3 different breast pump patterns.

Mother's perception regarding the comfort, rhythm, effectiveness, and ease of use of the three BPSPs will be assessed via a text message hyperlinked Qualtrics survey within 7 days of study completion. A reminder will be sent if no response in 7 days (Appendix K).

**Aim 4:** A fourth aim will compare proportion of feedings consisting of MOM consumed by infants between the 3 groups. Daily proportion of total feeds consisting of MOM consumed during the first 15 days and proportion of total feeds consisting of MOM consumed during the 24 hours prior to discharge will be recorded from the infant's EMR. Proportion of feeds that include MOM after discharge will be determined until the mother ceases lactation or the infant is 6 months old through monthly text message hyperlinked surveys through Qualtrics asking the total number of feeds in the past 24-hours that consisted of MOM (either direct breastfeeding or feeding expressed MOM).

**Exploratory Aim 1**: Will explore potential benefits of the three BPSPs on the lactation outcomes in Aim 1 and 2 of mothers with co-morbidities known to negatively affect lactation outcomes (high BMI/obesity, diabetes, pregnancy induced hypertension).  A subset of mothers diagnosed with high BMI/obesity, diabetes, and/or pregnancy induced hypertension will be classified as having 1, 2, or 3 risk factors known to negatively affect lactation outcomes. Potential benefits of the three BPSPs will be explored in this subset of mothers.

Exploratory Aim 2: Explore whether mothers identified as having faltering lactation who use an alternate BPSP (BPSP 1 or 2) achieve the same lactation success as mothers identified as not having faltering lactation (pumped MOM volume  $\geq 350$  mL/d by day 6-8). Lactation outcomes (see Aim 1 and 2) will be compared between mothers who were randomized to use either BPSP 1 or 2 and those mothers who were not randomized because they were not identified as having faltering lactation.

Confounding Variables. The following variables may affect pumped MOM volume in mothers of critically ill infants. While control of these variables within the study is impossible, we will carefully document these factors on all enrolled mothers to allow for inclusion in statistical analysis as adjustment variables. See **Table 1** for additional confounding variables.

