3. Duration of partial or exclusive MOM feedings after discharge	Monthly maternal text message with hyperlinked surveys through Qualtrics. (App J)	Monthly until lactation cessation or infant is 6 months of age.					
Length of NICU hospital stay; infant nutritional, and health outcomes	Days infant remained hospitalized in the NICU, nutritional and health outcomes	From birth until discharge.					
Covariates (1-6) below							
1. Demographic data	Maternal: Race/Ethnicity, delivery of > one infant, delivery mode, parity, BMI, co-morbidities. Infant : Gestational age at birth, birthweight, Apgar score. % of type of feeding consumed (MOM, donor human milk, formula). (App A, App N)	Upon entry into study and during the 15-day study period					
2. Number of pumping sessions per day	# of times a mother pumps her breasts per day. (App L)	Daily for 15 days					
3. Skin-to-skin care	Total minutes and episodes of skin-to-skin care.	Daily for 15 days.					

4. Maternal mood	Results of 2 MAACL-R tests completed by mom.	Prior to her hospital discharge and at 15					
	(App D)	days postpartum.					
5. Lactation experience	(a) Feeding plan prior to delivery, previous experience	Before maternal hospital discharge (a)					
	with breastfeeding and/or pumping, lactation intent, home	At end of study (b)					
	pump status (b) Lactation intent, lactation goals lactation						
	consultations, galactagogues, mastitis diagnosis and						
	treatment, use of hormonal birth control, home pump status						
	(App C)						

Table 2: Timeline of events over the 15-day study

Measure	0*	1	2	3	4	5	6	7	8	9	10	11	12	13	14	15
Consent, maternal interview		Х-	-X													
Pumping optimization		X-		-X			X-		-X							
MOM NA/K Level		Х-														- X
Lactation risk assessment							X-		-X							
Randomization							X-		-X							
Determination of CTV																X
Measures of pumped milk volume		X	X	X	X	X	X	X	X	X	X	X	X	X	X	X
Measures of infant consumption of MOM		X	X	X	X	X	X	X	X	X	X	X	X	X	X	X
Maternal perception survey (Part A)							Х-		-X							
Maternal perception survey (Part A/B)										Х-		-X				
MACCL			Х-	-X												X
Lactation experiences			X													X

\* = day of birth

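### Pumped volume before randomisation is absent from the covariates listed for adjustment, so the primary comparison may give up some precision that costs nothing to obtain

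*Protocol*

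**What the plan says.** **Test.** Sample Size Determination (protocol section 6) bases the trial on an "independent sample t-test comparison of means (adjusted for multiple comparison between 3 groups", "assuming a = 0.02 (Type I error rate), two-sided", and states that "with 30 mothers per group we will have 80% power to detect a difference of 300 ml". The Aim 1 text under Research Procedures and Analyses by Specific Aim describes how volume is measured and names no model.

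**Adjustment.** The Confounding Variables paragraph says that listed factors are recorded "to allow for inclusion in statistical analysis as adjustment variables" and refers to Table 1. The text then describes skin-to-skin care, lactation support and maternal mood. The covariate block of Table 1 shows demographic data (for the mother: "Race/Ethnicity, delivery of > one infant, delivery mode, parity, BMI, co-morbidities"), pumping sessions per day, skin-to-skin care, mood and lactation experience. The block is headed as having six items, and five are visible.

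**Early volume.** Mothers are randomised on day 6-8 if they have reached secretory activation and "have a pumped milk volume < 350 mL/d". Milk is weighed daily for 15 days in all mothers. The abstract describes the target group as mothers whose daily volumes already signal a high risk of not coming to volume. Aim 2 lists cumulative volume over days 1-7 among the outcomes to be compared. Randomisation is by blocks, with no stratification by volume mentioned.

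**The concern.** Where an outcome is also measured before randomisation, the baseline value is a natural covariate. It cannot be affected by treatment, it is often correlated with the outcome, and here it is collected anyway. Any variation in starting volume that carries through to days 8-15 otherwise stays in the residual, and a chance difference in starting volume between arms of 30 passes into the estimated effect.

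The list as written also mixes two kinds of covariate. Pumping sessions and skin-to-skin care are recorded over all 15 days and mood is measured again at day 15, so part of this information arises after randomisation and could be influenced by the assigned suction pattern. Pre-randomisation volume is free of that problem, yet it does not appear. At stake are the precision of the primary contrast and its sensitivity to chance imbalance. Its validity is not in question.

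**Working it through.** **Inputs from Sample Size Determination.** Difference 300 mL, SD 350 mL, stated effect size 0.84, 30 per arm, two-sided alpha 0.02, 80% power.

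**Step 1: the protocol's own figure.** For a two-sample t-test with n per arm, the noncentrality is d × √(n/2), with 2n − 2 = 58 degrees of freedom and a critical value of 2.392.

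- At d = 0.84: 0.84 × √15 = 3.253, power 80.3%. The stated 80% reproduces.
- At the unrounded d = 300/350 = 0.857: 0.857 × √15 = 3.320, power 82.0%. This is the unadjusted reference below. The mismatch between 0.84 and 0.857 is immaterial here.

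**Step 2: adding the baseline volume.** Let r be the within-arm correlation between pre-randomisation volume and days 8-15 volume. The protocol gives no value, so r is an assumption. The residual SD becomes 350 × √(1 − r²), and one covariate leaves 57 degrees of freedom (critical value 2.394).

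| Assumed r | Residual SD (mL) | 300 / residual SD | Power | Difference detectable at 80% power (mL) |
|---|---|---|---|---|
| none (unadjusted) | 350.0 | 0.857 | 82.0% | 293 |
| 0.2 | 342.9 | 0.875 | 83.7% | 287 |
| 0.3 | 333.9 | 0.899 | 85.8% | 280 |
| 0.5 | 303.1 | 0.990 | 92.1% | 254 |

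A second covariate (56 degrees of freedom), with no credit for any variance that it explains, changes the r = 0.3 result only from 85.8% to 85.7%.

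**Step 3: which r is plausible.** Entry restricts the baseline to below 350 mL/day, which limits the correlation. As an illustration, suppose that baseline is uniform on 0 to 350, that it carries through to the outcome with slope 1, and that the SD of 350 is on a daily scale.

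- Baseline SD = 350/√12 = 101 mL/day.
- r = 101/350 = 0.29, so the gain is close to that of the r = 0.3 row, about 4 percentage points.

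The protocol does not say whether 300 mL and SD 350 mL are daily or cumulative, so this is an illustration and not an estimate.

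**Step 4: chance imbalance under the same illustration.** The standard error of the between-arm difference in mean baseline is 101 × √(2/30) = 26 mL/day, so its 95% range is about ±1.96 × 26 = ±51 mL/day. At slope 1, an imbalance at the edge of that range would shift the contrast by about 51/300, or one-sixth of the target difference, if that target is daily.

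**The case against.** A reader might infer that the protocol has fixed an unadjusted t-test as its primary analysis and so discards its best predictor. The document does not support this. The t-test stands only in the power statement, which does not settle the final analysis, and the Confounding Variables paragraph already foresees covariate adjustment. The volume data are collected, so nothing is discarded. No correlation is reported, so early volume cannot be called the best available predictor.

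It can further be said that:

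- The final covariate set is commonly left to an analysis plan, which is not shown here. This is fair as far as the model is concerned. It does not remove the point, because the protocol writes out its own list and the visible list lacks this variable.
- The covariate block is headed as six items and five appear, so a sixth may have been lost when the table was converted to text. This stands, and it limits how firmly the omission can be asserted.
- The t-test is valid under randomisation, and its standard error already allows for chance imbalance. This stands too: Step 4 describes noise that adjustment could remove, not bias.
- The likely gain is modest. With entry truncated at 350 mL/day, 2 to 4 points of power is the cautious reading.
- A qualifying volume taken on day 8 could fall inside the days 8-15 outcome window. This is a real difficulty for a loosely worded remedy, and the fix below deals with it.

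**Conclusion.** The point holds as a missed improvement in precision. The covariates shown for adjustment omit pre-randomisation pumped volume, although the protocol measures it daily, uses it for entry and treats it as prognostic. The sample size is not wrong and the planned comparison is not invalid.

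On the protocol's planning figures, adjustment lifts power by about 2 points at r = 0.2, 4 at r = 0.3 and 10 at r = 0.5. These gains rest on an assumed correlation, a linear relation with a common residual variance, and 30 mothers analysed per arm. The entry cut makes the lower part of the range the more prudent expectation. The omission itself is subject to the possibility that the unseen sixth item in the covariate block is this variable. The change is still worth making, because the data already exist and even a small gain is useful where no allowance for dropout is stated.

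**What to change.** 1. Add a row to the Table 1 covariates: pumped volume over the last full 24 hours before randomisation.
2. State in the Aim 1 text that the primary days 8-15 comparison is a linear model on arm, with that baseline volume and the postpartum day of randomisation as covariates. The multiplicity adjustment across the three groups is unaffected.
3. Define the baseline and outcome windows so that they cannot overlap for a mother randomised on day 8.
4. Mark which Table 1 covariates are measured before randomisation and which run past it, and keep the latter out of the primary model.

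The cost is one table row, a few sentences and one or two degrees of freedom. No new data are needed and the sample size need not change.
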